## Algorithm for Prior / Concomitant Medications:

START DATE	STOP DATE	ACTION
Known	Known	If stop date <= study med start date, assign as prior If stop date >study med start date, assign as concomitant
	Partial	Impute stop date as latest possible date (i.e. last day of month if day unknown or 31 st December if day and month are unknown), then: If stop date <= study med start date, assign as prior If stop date > study med start date, assign as concomitant
	Missing	If stop date is missing could never be assumed a prior medication , assign as concomitant
Partial	Known	Impute start date as earliest possible date (i.e. first day of month if day unknown or 1 st January if day and month are unknown), then: If stop date <=study med start date, assign as prior If stop date >study med start date, assign as concomitant
	Partial	Impute start date as earliest possible date (i.e. first day of month if day unknown or 1 st January if day and month are unknown) and impute stop date as latest possible date (i.e. last day of month if day unknown or 31 st December if day and month are unknown), then: If stop date <= study med start date, assign as prior If stop date > study med start date, assign as concomitant
	Missing	Impute start date as earliest possible date (i.e. first day of month if day unknown or 1 st January if day and month are unknown), then: If stop date is missing could never be assumed a prior medication, assign as concomitant

START DATE	STOP DATE	ACTION
Missing	Known	If stop date <= study med start date, assign as prior If stop date > study med start date, assign as concomitant
	Partial	Impute stop date as latest possible date (i.e. last day of month if day unknown or 31 st December if day and month are unknown), then: If stop date <= study med start date, assign as prior If stop date > study med start date, assign as concomitant
	Missing	Assign as concomitant

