1.3 Study Design

This is an 8+8 weeks, randomized, double-blind, multi-center, placebo controlled, parallel group study to include adult patients with moderate to severe active Ulcerative Colitis. The study consists of an 8-week blinded treatment phase, followed by 8-week of blinded active arms extension phase. The primary endpoint is assessed at the end of treatment phase at week 8.

Eligible subjects will be randomized to either one of the 3 doses of active drugs or placebo in 1:1:1:1 ratio for 4mg QD, 4mg BD, 8mg QD and placebo group respectively for treatment phase. The total number of subjects to be randomized is 152. There will be a total of 9 outpatient clinic visits. Subjects randomized into placebo in treatment phase will also have a pre-assigned randomized treatment sequence for extension phase, which are 3 active groups (placebo -> 4mg QD, placebo -> 4mg BD, and placebo -> 8mg QD) in a 1:1:1 ratio. Subjects randomized to the active arms for treatment phase will remain in the same dose group in the extension phase.

At Visit 1 (screening), subject will be screened and if the subject meets the inclusion/exclusion criteria, the subject can be consented and enrolled into the study with a subject identifier number.

At Visit 2 (Day 0), subject will be randomized into the study if there is no further change to subject's criteria.

After randomization, the subject will be followed-up at week 1, week 4, and week 8, corresponding to Visit 3, Visit 4, and Visit 5 at treatment phase respectively. At Visit 5 (week 8) the primary endpoint assessment will be conducted. Following this treatment phase, subjects have the option to enroll into a further 8 weeks of active arms extension phase.

All subjects that have completed the initial 8 weeks (non-responders or responders) have the option to enter a blinded active arm 8-week extension phase according to the group they were randomized to for extension phase. All subjects have the option not enrolling into the extension phase after first 8 weeks of treatment. All subjects in the extension phase are followed-up for further 2 weeks until week 18 (last visit). Subjects who have completed the first 8-week of treatment phase, but decided not entering into extension phase are required to attend the 2-week follow-up visit. Early withdrawn subjects during the first treatment phase cannot enter the extension phase.

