6.6 Concomitant Medications

6.6.1 Permitted Concomitant Medications

All concomitant medication(s) taken during the trial must be recorded with indication, daily dose, and start and stop dates of administration. All subjects will be questioned about concomitant medication at each clinic visit. Following therapy for ulcerative colitis are allowed providing they are stable for the specified period of time:

- Oral 5-ASA or sulfasalazine are allowed providing that the dose is stable for at least 2 weeks prior to baseline and during the study treatment period.
- Oral steroids are allowed during the study up to the dose of 30 mg/day of prednisolone or equivalent, providing that the dose has not been commenced or changed within 2 weeks of baseline and until to the end of treatment phase (Week 8). During the treatment phase, if the subject cannot tolerate the oral steroids dose or there is a significant safety risk associated with continued use of the steroids, the dose may be reduced at the discretion of the investigator and the reasons for dose reduction need to be documented in the medical records. During the extension phase, tapering of the oral steroid dose can be commenced for subjects at investigator's discretion. Tapering scheduled treatment is provided as below:
 - Subjects receiving > 10 mg/day prednisolone or equivalent: taper dose by 5 mg/week until a 10 mg/day dose (or equivalent) is reached, then continue tapering at 2.5 mg/week until 0 mg/day.
 - Subjects receiving ≤ 10 mg/day prednisolone or equivalent: taper dose by 2.5 mg/week until 0 mg/day.

If subject experiences worsening of signs or symptoms during the tapering schedule, in the opinion of the investigator, due to reduction in oral steroid daily dose, the daily oral steroid dosage for the subject could be reverted to the preceeding daily dosage instructed by the investigator, but should not exceed Baseline dose.

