Prior and concomitant medications will be coded using the World Health Organization Drug Dictionary and will be grouped by PT. The summary tables will show the number and percentage of subjects by PT, for all subjects overall. Prior medications are those medications that were stopped prior to first study treatment. Concomitant medications are medications taken at least once after first study treatment. Medications stopped on the same day as first study treatment will be considered as prior medication only. Only concomitant medications will be summarized. Prior medications will be listed only. Prior and concomitant medications will be listed separately. For the summaries of concomitant medications, subjects who take the same medication (in terms of the PT) more than once will only be counted once for that medication.

Physical examination and pregnancy data will be listed only.

10. Study Conduct Considerations

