## 12. MEDICATIONS AND PROCEDURES

Prior medications are those medications that were stopped prior to first study treatment. Concomitant medications are medications taken at least once after first study treatment. Medications stopped on the same day as first study treatment will be considered as prior medication only.

Prior and concomitant medications will be coded using the World Health Organization Drug Dictionary (WHO Drug Global 01Sep2018\_B3). The PT and Anatomical Therapeutic Chemical (ATC) Classification System level 2 will be used for tabulation. The summary tables will show the number and percentage of patients by PT and ATC level 2, for each treatment group and overall. Only concomitant medications will be summarized. The descriptive summaries for concomitant medications will be presented for the SS. Missing or partial dates for medications will be handled according to Appendix 2 of this analysis plan. In the case where it is not possible to define a medication as prior or concomitant, the medication will be classified by the worst case; i.e. concomitant. For the summaries of concomitant medications, patients who take the same medication (in terms of the PT), more than once will only be counted once for that medication. Prior medications will be listed only.

The detailed information of prior and concomitant medication use including medication name, start date, end date, ongoing or not, primary reason for use, total daily dose, frequency and route of administration, etc. will be listed. Prior and concomitant medications will be listed separately.

The detailed information of procedures will be collected on the “Procedures” form of Electronic Case Report Form (eCRF) including procedure name, start date, end date, ongoing or not, and primary reason for use. Procedure name will be coded using Medical Dictionary for Regulatory Activities Version 21.1 or higher version. Procedures information be will be listed.

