## 13. STUDY MEDICATION EXPOSURE

Exposure to study medication will be presented for SS by treatment group.

The date of first study medication administration will be taken from eCRF “Noncompliance with study treatment ” form if available (Site will check medical chart and make the first dose record on this eCRF form). In case of not available, the first dose date from the diary data will be used. The date of last study medication will be taken from the eCRF “End of Treatment”

Document: \\ieedc-vnasc01\Biosdata\Reistone\SHR0302\CZA55021\Biostatistics  
Author: [REDACTED]

Version Number:  
Version Date:

Final v1.2  
23Mar2021

Template No: CS\_TP\_BS016 Revision 5  
Effective Date: 01Apr2018

Reference: CS\_WI\_BS005

form. In the case of missing data on the eCRF, the last dose date from diary data will be used

The study medication intake for each day will be taken from the diary “Time of Dosing” and “# Tablets Taken” items. The following information will be summarized for each treatment group in treatment phase, extension phase and overall:

- Duration of Exposure (days)
- Planned number of study drug tablets
- Actual number of study drug tablets
- Number of Dosing Days
- Cumulative Dose (mg)
- Average Daily Dose (mg/day)

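### The concomitant-medication tables carry no study phase, so drugs first started on SHR0302 after Week 8 count under placebo and the by-arm summary cannot isolate the controlled 8 weeks (minor, descriptive only)

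*SAP*

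**What the plan says.** SAP 12 defines the class by first dose only: "Concomitant medications are medications taken at least once after first study treatment". SAP Appendix 2 applies this through the stop date: "If stop date >study med start date, assign as concomitant"; a missing stop date also gives concomitant. A drug stopped on the day of first dose is prior. Neither place tests a date against Week 8, Week 16 or the last dose.

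On presentation, SAP 12 says: "The summary tables will show the number and percentage of patients by PT and ATC level 2, for each treatment group and overall". It adds: "Only concomitant medications will be summarized". Prior medications are listed only. The protocol (9.3.4.4) plans the summary with neither arm nor phase: "The summary tables will show the number and percentage of subjects by PT, for all subjects overall".

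The design has two unlike phases (Protocol 1.3): "The study consists of an 8-week blinded treatment phase, followed by 8-week of blinded active arms extension phase". The extension is optional. Placebo patients who enter it go to one of the three SHR0302 regimens, and active patients keep theirs. The Time and Event Table (Protocol 5.12) has concurrent medication assessed at every visit to Week 18.

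Other data in the same SAP are split by phase. For exposure (SAP 13): "The following information will be summarized for each treatment group in treatment phase, extension phase and overall". Compliance (SAP 14) is split into treatment and extension phase, and Appendix 2 assigns treatment-emergent adverse events to treatment, extension or follow-up by the Week 8 and Week 16 visit dates.

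**The concern.** The SAP recognises elsewhere that placebo patients change treatment at Week 8. SAP 16.1.1 and Appendix 1 create a placebo group limited to the treatment phase, and pooled dose groups that take in the switched patients. Appendix 1 assigns these only to adverse-event and ECG tables. Medication tables fall back on the default groups, where placebo means initial randomisation, and the three placebo-to-active columns also run across both phases.

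At stake is a plain descriptive question: did arms differ in therapy newly started before the Week 8 endpoint? It has some bearing on the primary result. The failure rule in SAP 15.1.1 covers non-completion and missing subscores, and the SAP states no rule for patients who take a prohibited drug. The deviation summary in SAP 9 is by type of deviation, with no phase stated. Because the extension is optional, arms with different uptake would also contribute different observation time to a table of simple counts and percentages.

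**Working it through.** The plan gives no figure here to reproduce. The check applies the stated rules to cases, then sizes the mixing.

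**1. The rule on test cases.** First dose is day 0, Week 8 is day 56 and Week 16 is day 112 (Protocol 5.12). The last column applies the SAP's adverse-event cut-points to the start date.

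| Drug use | Current medication rule | Phase by adverse-event cut-points |
|---|---|---|
| Stopped day 0 | prior | not applicable |
| Days 21–25 | concomitant | treatment |
| Days 70–80 | concomitant | extension |
| Days 115–120 | concomitant | follow-up |
| Started day 118, no stop date | concomitant | follow-up |

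The last four are indistinguishable in the tables.

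**2. Which column they enter.** For a placebo patient who continued, the drug used on days 70–80 was first taken on SHR0302, yet it counts under placebo, or under a placebo-to-active column that does not separate the phases. For an active-arm patient the column names the right treatment, and only the period is mixed.

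**3. Time covered.** For a patient who enters the extension, 8 + 8 + 2 = 18 weeks. Controlled phase: 8/18 = 44%. Later: 10/18 = 56%, of which follow-up is 2/18 = 11%. A patient who completes Week 8 and does not continue has 8 + 2 = 10 weeks, of which 2 are later.

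**4. Illustration of dilution.** All rates are assumed; the documents give none. Let e be the share newly using a drug class before Week 8 and l the share using it later. The table shows 1 − (1 − e)(1 − l) if early and later use are independent, max(e, l) if the smaller group lies wholly within the larger, and e + l if no one is in both.

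| Early use, dose v placebo (ratio) | Later use, both | Independent | Full overlap | No overlap |
|---|---|---|---|---|
| 20% v 10% (2.0) | 20% | 36% v 28% (1.29) | 20% v 20% (1.00) | 40% v 30% (1.33) |
| 20% v 10% (2.0) | 10% | 28% v 19% (1.47) | 20% v 10% (2.00) | 30% v 20% (1.50) |
| 30% v 10% (3.0) | 20% | 44% v 28% (1.57) | 30% v 20% (1.50) | 50% v 30% (1.67) |

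For example, 1 − 0.8 × 0.8 = 0.36, 1 − 0.9 × 0.8 = 0.28, and 0.36/0.28 = 1.29. An early ratio of 2.0 can thus appear as anything from 1.00 to 2.00, depending on assumptions that the table gives no means of checking. Lower uptake weakens the effect: if half of each group continue, 20% of those use the drug later and no one else does, later use is 0.5 × 20% = 10%, which is the second row.

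**The case against.** The strongest reply is that this is a descriptive safety table that feeds no test, estimate or analysis set; that Appendix 2 faithfully implements the definition in SAP 12 and the protocol; and that the listings give start and end dates, so use before Week 8 can be recovered. All of that stands, and it sets the severity. It does not supply the missing summary: a listing is not a by-arm comparison. The table templates mentioned in SAP 8 are not among the documents and might carry a split, but the text states none, though it does for exposure, compliance and adverse events.

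Four stronger readings are tempting and are not supported.

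- A reader might infer that the table hides steroid changes, since Protocol 6.6.1 says: "During the extension phase, tapering of the oral steroid dose can be commenced". But SAP 12 counts a patient once per preferred term and shows no dose. Background steroid or 5-ASA users are concomitant from the first dose with or without a split, and a split table would not show a taper.
- A reader might infer that UC rescue therapy during follow-up inflates the counts. Protocol 6.7 keeps post-treatment UC therapy out of the eCRF, so the follow-up part concerns mainly other drugs.
- A reader might infer that treatments are mixed in every arm. That happens only for patients randomised to placebo.
- A reader might infer bias in the primary analysis. Nothing in the medication table enters it.

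**Conclusion.** The gap is real and minor. As written, the medication summary credits to placebo some drugs first started on SHR0302, and in the active arms it merges the controlled 8 weeks with up to 10 later weeks. It cannot show whether newly started therapy differed between arms before the Week 8 endpoint. The size in this trial cannot be derived from the documents; the dilution figures above are illustrations, and those in the independent column also assume that early and later use are unrelated and that everyone continues. The conclusion rests on the SAP text, without sight of the table templates.

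**What to change.** Amend SAP 12 and the Appendix 2 medication algorithm together, since the open-ended definition is in both.

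- Assign each concomitant drug to treatment, extension or follow-up by the Week 8 and Week 16 visit dates already used for adverse events, so that one phase definition serves the whole SAP. Count a drug in every phase its use overlaps; the adverse-event rule uses onset only, which is not enough here.
- For patients who stop study drug early, keep therapy started before their Week 8 or early withdrawal visit in the treatment-phase table, flagged as started after last dose. A cut at last dose would remove therapy from the very period of interest.
- For patients who complete Week 8 but do not continue, assign later starts to follow-up.
- Present a treatment-phase table by the four randomised arms and an extension table by the drug actually taken. List follow-up medications separately, noting that post-treatment UC therapy is not collected.

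No new data are needed. The cost is one more table, a few lines of text, and phase imputation for partial dates, for which the adverse-event algorithm already gives a pattern.
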